# WEEK 24+0 – 30+6 GESTATION VISIT

At one of the monthly visits, which occurs at or between 24+0 and 30+6 weeks gestation. A 75g OGTT (baseline and 2 hour sample) will be performed (as per the working practice document) and stored locally for future investigations.

Prior to the visit, the woman will be given written information and have this read to her (if applicable) which ask her to fast (take no food, only water) for a period of 8-12 hours before the appointment. With the exception of the 75g glucose load, the woman will remain fasted until after the 2 hour blood sample is taken.

The results of the glucose tolerance test is not a routine test, and the results will be concealed from the woman and from her caregivers until the end of the study. An additional OGTT (outwith the trial) can be performed for clinical reasons at any time if required by the local physician. If a participant develops gestational diabetes during the study, she will be asked to stop the study treatment (IMP) and will be referred to her obstetrician for further advice and treatment, which may include diet metformin and/or insulin. The details of any treatments and reasons for stopping the IMP will be recorded in the eCRF. Following local procedures the clinical care team may also conduct tests to identify other pregnancy related diseases such as a blood pressure monitoring, urine test strip and blood samples to screen for e.g. pregnancy induced hypertension, pre-eclampsia or anaemia. Any diseases identified in a participant/ fetus/ baby will be recorded following the adverse events reporting.

# LABOUR and DELIVERY

Admission for delivery will not be a formal study visit and as it is anticipated it will not be recorded as an SAE. Information will be obtained usually from the woman's medical notes on the maternal outcomes of delivery, including method of delivery, indication for delivery method, date and gestation of delivery and blood loss.

Information on the previous 4 weeks' pregnancy and labour and delivery complications will be collected. Adverse events (AE) will be recorded in the patient notes and on the

eCRF. Serious adverse events (SAEs) will be recorded on the SAE form and in the eCRF. All unused study medication returned and sent to pharmacy for recording compliance. The participant diary will be collected and data entered on the eCRF.

The baby outcomes of delivery including baby weight, gender, and birth outcome (e.g. live birth, stillbirth or death in the delivery room) will be collected and recorded by local investigators mainly from hospital notes, and the data will be entered on to the eCRF.

#### NEONATAL and 28(+7) DAY POSTNATAL VISIT

Either participants visit the hospital to meet face to face with staff, or staff may visit the woman at her home or local clinic. The woman will be thanked for her involvement and further data collected about both her and her babies' well-being since delivery, this will be in the form of a short questionnaire (in English and Chichewa). The questionnaire will be read to her and her answers translated and recorded on the eCRF.

SAE's will be recorded up to 28days after birth. Events which have not resolved at study completion will be reviewed prior to database lock and a resolution sought where possible. We will also ask women for permission to invite them and their babies for some future studies.

End of trial participation will be recorded in the eCRF and (if available locally) the medical notes.

#### TRAVEL REIMBURSMENT

Women will be recompensed travel cost as per Government recommendations for each study visit, which is additional to normal antenatal care. It is anticipated women would usually attend three antenatal visits routinely between booking for care and delivery.

Women are expected and encouraged to deliver in hospital and this will not be a considered a study visit. The postnatal (28 day visit) visit would be study specific visit.

#### END OF STUDY PROCEDURES

At the end of the study, the results of the oral glucose tolerance test taken in pregnancy will be fed back to the participant's health care provider.

# TABLE OF STUDY VISITS

Pregnancy gestation	1	2 +0 to 28	*  weeks	16, 20, 32, 36,40 weeks	24-30Weeks	Labour Delivery/	Neonatal/ 28 day postnatal
	Screenin	gConsen	Randomisation	Monthly	Study visit	Study visit	
Inc/Exc Criteria	х						
Patient Information Leaflet	х						
Consent Form		Х					
Demographics		x					
Medical History		Х					
Height and Weight		Х					
Vital Signs		x		x	х	х	
Confirm eligibility		x					
Randomisation			x				
Study Drug dispensed			х	x	х		
Review Patient Diary (collect at Delivery)				x	х	х	
Complete side effects questionnaire on eCRF				x	х	х	
Review and record pregnancy complications				x	х	х	
Review SAE's				x	х	х	x
Fasted glucose tolerance test (sampling at baseline and 2 hrs)					х		
Stored sample for inflammatory markers etc					х		
Unused Study Drug /packaging returned				x	х	х	
Labour/Delivery Information						х	
Neonatal/28 day postnatal complications and questionnaire							X

# **10. COMPLIANCE ASSESSMENTS**

Treatment Compliance will be recorded in diary as described in paragraph 8.5.

### 10.1 STORAGE AND ANALYSIS OF SAMPLES

Samples will be collected and stored as per local SOP in local Laboratories. Blood samples for the glucose tolerance test will be processed and then stored in the laboratories of the recruiting sample. Analysis for glucose will be performed after the last patient last visit is complete and any remaining blood discarded.

An additional aliquot of blood will be sent to the laboratories at MEIRU for storage and future analysis of inflammatory markers (and other analytes to be determined). These samples will be stored for 5 years. It is not anticipated that any blood samples will be shipped out of Malawi.

#### **10.2 DATA COLLECTION**

Data will be collected by the trial team from the participant verbally and confirmed where possible in the medical records including demographics, details of current and previous pregnancies, contact details, information about blood test collections, labour and delivery outcomes, and neonatal / postnatal outcomes. Participants will be asked about their well-being at each post-randomisation visit to identify side effects and any adverse events for reporting. We will also review diaries for compliance, acceptability and side effects. Results of study blood tests for glucose tolerance testing locally will remain concealed from the participant and her clinician until the trial is completed.

# **10.3 SOURCE DATA DOCUMENTATION**

Source documents are original documents, data and records where source data are recorded for the first time. This is all information entered directly in to original records (mother and baby) and certified copies of original records or clinical findings, observations, or other activities in a clinical trial necessary for the reconstruction and evaluation of the trial.

Data will be derived from the participant's own and their baby's medical records, history from the patient, medication charts, study diary, postnatal questionnaire and laboratory results. All study data will be transcribed on to the eCRF by the recruiting team or by a data clerk based in Malawi. All study data will be entered by authorised and delegated individuals. All electronic data collected will be held securely locally. A copy of an anonymised database will be transferred to the Edinburgh Clinical Trials unit at intervals to be described. Patient identifiers will not be transferred outside Malawi. A separate data management plan will be generated to describe management of the data in more detail.

For the purpose of study archiving the eCRF will be considered source data and archived according to ECTU policies.

# 10.4 CASE REPORT FORMS

All case report forms (electronic) for this study will be approved by the study sponsors prior to use (as per SOP CR013 eCRF Design and Implementation) and by the ethics committee.

#### 10.5 TRIAL DATABASE

The trial database will be developed and managed by the Edinburgh Clinical Trials Unit. The database will be hosted on servers based at the Malawi Epidemiology and Research Unit (MEIRU). The full trial database will contain patient identifiers to facilitate future follow up. Participants will be asked to consent to this at recruitment. Patient identifiers will only be visible to clinicians entering the data and to nominated data clerks in Malawi.

A copy of an anonymised subsection of the database will be transferred to the Edinburgh Clinical Trials Unit at intervals for analysis. On completion of the study, Edinburgh will store the final version of the anonymised subsection of the database for an indefinite period. The Malawi Epidemiology Research Unit will store the original version of the database (with identifiers) indefinitely. On completion of the study and publication of study results, anonymised data may be shared with other researchers upon request, in line with MRC guidelines.

#### 11. STATISTICS AND DATA ANALYSIS

#### 11.1 SAMPLE SIZE CALCULATION

Sample size. It is not possible generate a formal sample size calculations for feasibility studies, Our proposed sample size is based on the 30-50 per arm recommended for feasibility studies by some funders (National Institute for Health Research) (Chief Scientist Office). The feasibility study described here will be used to determine whether a large randomised trial is warranted and feasible. The remaining outcomes will be used either as safety markers, and will allow an estimate of the prevalence of gestational diabetes and pregnancy hypertensive disorders – all of which will inform the design of a large randomised trial.

PAPAGENO is the first cTIMP by the Chief Investigator in Malawi, and we anticipate that recruitment strategies may require refinement during the pilot before they are fully effective. Hence we plan to recruit at the upper end of the sample size recommended for feasibility studies - 50 per arm (i.e. 100 women in total), to allow us to properly test the feasibility of the study in this novel setting. We anticipate that the first 50 recruits will be used to implement and refine recruitment strategies, and the final 50 recruits will be used to properly determine recruitment rate.

Dropout rates, assumptions and justification. The drop out rate in our previous (UK) trial of metformin in pregnant women was less than 5 % (Chiswick, Reynolds et al. 2015). This is significantly lower than the average drop out rates in clinical trials which approach 30% (Centrewatch news online 27th June 2016). We anticipate that the drop out rate in this trial might be as high as the average, leaving 70 women with usable data at the end of the study.

Recruitment period assumptions and justification. We will recruit over a 12 month period, with follow up (to the end of pregnancy and the neonatal period) over a further 6 months. Recruiting over 12 months requires a recruitment rate of 8-9 women per month. Most of the recruitment will occur in one site. Over 100 new pregnant women are seen each week in this recruiting sites. Hence we are confident that sufficient women are available for recruitment. Failure to recruit 100 women in 12 months will imply that the study is not possible as currently configured. We will also attempt to recruit in a second site. Recruitment in this second site will be considered exploratory only, and will not inform the recruitment rate described below.

#### 11.2 PROPOSED ANALYSES

The primary outcome is the ratio of women recruited, expressed as a fraction of the total number of women attending for antenatal care over the recruitment period. We will report this separately for the first 50 women, and the final 50 women in the primary recruiting site. The ratio of women recruited, expressed as a fraction of the total number of women attending for antenatal care over the recruitment period for the final 50 women in the primary recruiting site will be used to inform the timelines for a substantive trial.

Within the placebo group, we will determine the prevalence (with 95% confidence limits) of each of gestational diabetes and pregnancy induced hypertension.

We will generate mean (SD) or incidence of secondary outcomes overall, and in each of the two treatment groups. No formal statistical comparisons will be made between the two treatment groups, given the limitations of study power. A formal statistical analysis plan will be generated prior to study unblinding.

#### 11.3 STOPPING RULES

We have set the following safety rules for PAPAGENO based on maternal and neonatal deaths that are possibly or definitely related to IMP. We have based these rules on the expected frequency of maternal and neonatal deaths in the population.

Maternal death rate in Malawi is 634 per 100,000 (UNICEF 2015). The combined stillbirth and neonatal death rate in Malawi is 44 per 1000 births (UNICEF 2015). With these expected death rates, we consider that a trebling of this rate would be grounds for serious concern. If such deaths were thought to be related or possibly related to study IMP, that will prompt a halt in recruitment pending review by the independent Data Monitoring and Safety Committee (iDMSC).

Our stopping rules will be based on the number of deaths expected within the first 25, 50 and 100 women recruited. The table below shows the number of expected deaths, and the number within each recruitment band that will trigger a rapid review by the iDMSC. The iDMSC will convene to review data within 14 working days. All the deaths are considered to be related, recruitment will be halted pending the iDMSC. If one or more of the deaths is considered unrelated, recruitment will continue pending review by the iDMSC. Whether or not the deaths are considered related, already recruited to the trial will continue on allocated IMP, pending the iDMSC review. The iDMSC will review unblinded data and advise whether the trial should be stopped, or the circumstances under which the trial should continue.

Number of women recruited	Expected number of maternal deaths	Number of maternal deaths that will trigger a halt to further recruitment.	Expected number of combined stillbirths and neonatal deaths	Number of combined stillbirths and neonatal deaths that will trigger a halt to further
Up to 25	Less than 1 (0.158)	1	1.1	recruitment. 3
Up to 50	Less than 1 (0.317)	1	2.2	6
Up to 100	Less than 1 (0.634)	2	4.4	13

The most serious adverse effect of metformin is lactic acidosis, with an estimated frequency of 4 per 100,000. In a sample size of 100, we would expect 0.0004 cases of lactic acidosis. Any events of lactic acidosis will prompt a review by the iDMSC within 14 working days. If lactic acidosis is considered related to the study medication, recruitment will halt temporarily, pending review by the iDMSC. If lactic acidosis is not considered related, recruitment will continue, pending review by the iDMSC. Those already recruited to the trial will continue on allocated IMP pending iDMSC review. The iDMSC will review unblinded data and advise whether the trial should be stopped, or the circumstances under which the trial should continue.

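### Section 11.3 contradicts itself on which deaths count towards the triggers and on what a trigger does, and thresholds of three times all-cause rates fit only an all-cause count

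*Protocol*

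**What the plan says.** All of the relevant text is in Protocol section 11.3 (Stopping rules).

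- **Which deaths.** The section begins "We have set the following safety rules for PAPAGENO based on maternal and neonatal deaths that are possibly or definitely related to IMP". The next sentence gives a different basis: "We have based these rules on the expected frequency of maternal and neonatal deaths in the population".
- **Benchmark.** "Maternal death rate in Malawi is 634 per 100,000 (UNICEF 2015") and "The combined stillbirth and neonatal death rate in Malawi is 44 per 1000 births (UNICEF 2015"). Both are population rates with no causality condition.
- **Level of concern.** "With these expected death rates, we consider that a trebling of this rate would be grounds for serious concern".
- **Halt, first statement.** "If such deaths were thought to be related or possibly related to study IMP, that will prompt a halt in recruitment", pending committee review.
- **Review.** The table is introduced as showing "the number within each recruitment band that will trigger a rapid review by the iDMSC". The committee is to convene within 14 working days and see unblinded data. Recruitment stops in the meantime if all the deaths are judged related, and continues if one or more is judged unrelated.
- **Table.** Expected maternal deaths are 0.158, 0.317 and 0.634 at 25, 50 and 100 women, with triggers 1, 1 and 2. Expected stillbirths plus neonatal deaths are 1.1, 2.2 and 4.4, with triggers 3, 6 and 13. The column headings describe these as numbers that halt further recruitment.

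**The concern.** A count and its threshold should refer to the same events. A national death rate has no subset of deaths related to study drug. If metformin does no harm, the number of truly drug-related deaths is about zero, not 4.4. If it trebles mortality, the drug-related deaths are the excess, twice the background, yet on the opening sentence they would have to reach three times the background.

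The section also gives two consequences for the same numbers. The sentence before the table says review, and the table headings say halt. A site, or whoever writes the committee charter, could follow the opening sentence and count related deaths only, or follow the later text and count all deaths. At stake is whether the mortality safeguard responds to the trebling it was set up to catch.

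**Working it through.** **Inputs, all from section 11.3.** Background rates are 634/100,000 = 0.00634 per woman and 44/1000 = 0.044 per birth. The rate ratio of concern is 3, the bands are 25, 50 and 100 women, and the triggers are 1/1/2 and 3/6/13.

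**Step 1: reproduce the table.** Expected count = n × rate, and the trigger is about three times that.

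| Women | Maternal expected | ×3 | Trigger | Stillbirth + neonatal expected | ×3 | Trigger |
|---|---|---|---|---|---|---|
| 25 | 0.1585 | 0.48 | 1 | 1.1 | 3.3 | 3 |
| 50 | 0.317 | 0.95 | 1 | 2.2 | 6.6 | 6 |
| 100 | 0.634 | 1.90 | 2 | 4.4 | 13.2 | 13 |

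The table reproduces. Its thresholds are three times the all-cause rates, rounded to whole numbers.

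**Step 2: each look taken singly.** The chance of reaching trigger t among n women is P(X ≥ t) with X ~ Binomial(n, r). With trebling in all women, r is:

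- all deaths counted: 3 × 0.044 = 0.132 and 3 × 0.00634 = 0.01902;
- only the excess counted as related: 2 × 0.044 = 0.088 and 2 × 0.00634 = 0.01268.

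| Women | Stillbirth + neonatal, all deaths | Excess only | Maternal, all deaths | Excess only |
|---|---|---|---|---|
| 25 | 66% | 38% | 38% | 27% |
| 50 | 66% | 28% | 62% | 47% |
| 100 | 57% | 10% | 57% | 36% |

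**Step 3: any of the three looks.** The rule can act at 25, 50 or 100 women, so the chance of at least one crossing is the fairer measure.

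For maternal deaths, no crossing means no death in the first 50 women and at most one in the next 50. The chance of a crossing is therefore 1 − (1−r)^50 × [(1−r)^50 + 50r(1−r)^49].

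- All deaths, r = 0.01902: 1 − 0.383 × (0.383 + 0.371) = 71%.
- Excess only, r = 0.01268: 1 − 0.528 × (0.528 + 0.339) = 54%.

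For stillbirths plus neonatal deaths, the same calculation carries forward the distribution of counts that have not yet crossed.

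- All deaths: 82%.
- Excess only: 46%.

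**Step 4: background deaths judged related.** The protocol does not say what share f of background deaths would be called possibly related, so f is an assumption. The counted stillbirth-plus-neonatal rate is then 0.088 + 0.044f.

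| f | Counted rate | Any-look chance | At 100 women only |
|---|---|---|---|
| 0% | 0.088 | 46% | 10% |
| 25% | 0.099 | 56% | 19% |
| 50% | 0.110 | 66% | 30% |
| 75% | 0.121 | 75% | 44% |
| 100% | 0.132 | 82% | 57% |

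**Step 5: no drug effect, all deaths counted.** Stillbirths plus neonatal deaths reach their trigger with chance 10%, 2.2% and 0.05% at the three looks (any look about 10%). Maternal deaths do so with chance 15%, 27% and 13% (any look about 30%).

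**The case against.** A reader might infer that the triggers count only deaths judged related, and that a true trebling would therefore usually be missed, with 90% missed at 100 women for stillbirths plus neonatal deaths. The documents do not support that, for three reasons.

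- **The review text is not limited to related deaths.** It sets no relatedness condition, and it provides for counted deaths that turn out to be unrelated, which makes sense only if they are counted. The lactic acidosis rule later in 11.3 works the same way: any event prompts review, and relatedness decides only whether recruitment pauses. On that reading, the review count and its benchmark agree.
- **The 90% figure is the weakest single look.** Over all three looks, the excess-only count misses about 54% of the time for stillbirths plus neonatal deaths, and the maternal trigger is reached more often than not.
- **Excess-only counting assumes perfect attribution.** Sections 12.4 and 12.5.2 have blinded assessors judge every event as if the woman were on metformin, with a broad category of possible relatedness. Some background deaths would probably be included, by an unknown amount.

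There are also backstops. Section 12.1 makes deaths reportable whatever their relationship to the drug, and section 9.1 gives the committee interim unblinded outcome data.

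These points limit the finding but do not remove it. The opening sentence introduces the rules that follow and names related deaths. The first halt sentence repeats the condition. The table headings attach a halt to numbers that the text attaches to a review. Blinded attribution makes the sensitivity of a related-only count unknown; it does not bring the count into line with its benchmark.

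**Conclusion.** The concern holds as an internal contradiction with a measurable consequence. Section 11.3 does not settle which deaths are counted or whether reaching the count means a review or a halt, and its thresholds match only an all-cause count. If the opening sentence governs and only the excess is counted, the any-look chance of responding to a trebling falls from about 82% to 46% (stillbirths plus neonatal deaths) and from about 71% to 54% (maternal). If 25% to 75% of background deaths are also judged related, the first figure is about 56% to 75%. If the later review text governs, this loss does not arise for the review.

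Assumptions: trebling in all women, one birth per woman, complete follow-up of the women in each band, independent events, and cumulative counts. A trebling confined to the metformin half would give lower chances under either definition. That is a separate matter and is left out of these figures.

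**What to change.** In section 11.3 and the committee charter, reconcile the opening sentence, the first halt sentence, the text before the table and the table headings:

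1. State that the deaths counted against 1/1/2 and 3/6/13 for committee review are deaths from any cause, so that the count matches its benchmark.
2. State separately, and in the same terms throughout, what part relatedness plays in a recruitment halt. Which halt rule applies is for the sponsor and the committee to settle. The distinction between halting and continuing should not be lost by accident when the count is redefined.
3. Do not present three times the all-cause rate as the threshold for a related-only count.

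The change needs no extra participants or data. Compared with a related-only count, it brings more reviews when the drug does no harm: an any-look chance of about 10% for stillbirths plus neonatal deaths and about 30% for maternal deaths. If the table headings still say halt, those same chances would apply to recruitment halts, so the headings must be corrected together with the count.

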# 7. RANDOMISATION

#### 7.1 Randomisation Procedures

Participants will be randomised to treatment (active or placebo) in a 1:1 ratio. Recruiting centre will be the only stratification variable, using simple randomisation under a randomly permuted block design. Randomisation codes will be provided by ECTU to ISG and packs dispensed in a sequential fashion. Details of the study pack number allocated will be recorded in the participant's medication record as well as in the drug accountability logs.

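### Section 11.3 names a trebling of drug-related deaths as the level of concern, but its triggers treble the count over both arms, which corresponds to about a fivefold rate on metformin at the final triggers

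*Protocol*

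**What the plan says.** Protocol section 11.3 limits its safety rule to maternal and neonatal deaths that may be related to the study drug. It takes the national rates as background: 634 maternal deaths per 100,000, and 44 stillbirths plus neonatal deaths per 1000 births. It then fixes the level of concern: "With these expected death rates, we consider that a trebling of this rate would be grounds for serious concern".

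The count is taken over everyone recruited: "Our stopping rules will be based on the number of deaths expected within the first 25, 50 and 100 women recruited". The last row of the table reads "Up to 100 Less than 1 (0.634) 2 4.4 13", that is, 0.634 maternal deaths expected with a trigger of 2, and 4.4 stillbirths plus neonatal deaths expected with a trigger of 13. No trigger is given by arm. Reaching a trigger leads to rapid iDMSC review of unblinded data, and recruitment halts meanwhile only if all the deaths are judged related.

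Section 7.1 states: "Participants will be randomised to treatment (active or placebo) in a 1:1 ratio". Section 11.1 plans 50 women per arm.

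On lactic acidosis, section 11.3 gives a frequency of 4 per 100,000 and concludes: "In a sample size of 100, we would expect 0.0004 cases of lactic acidosis".

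**The concern.** The criterion is about harm from the study drug, and only women on metformin can be harmed by it. The triggers treble the expected count in metformin and placebo women together. The placebo half dilutes the signal, so the rate on metformin that corresponds to a trigger is well above three times background.

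At stake is whether the table acts at the level of harm that the protocol itself calls serious, in a trial where the outcomes are maternal and perinatal deaths.

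**Working it through.** **Inputs.** Background rates p = 0.00634 (maternal) and 0.044 (stillbirth plus neonatal), and bands of N = 25, 50 and 100 women, all from section 11.3. Allocation is 1:1 (section 7.1). Assumptions: placebo stays at background, one baby per woman, every woman's outcome is known, and all deaths count.

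**Reproducing the table.** Expected = N × p, with N counting both arms.
- Maternal: 0.158/0.317/0.634. Three times this is 0.48/0.95/1.90, rounded up to 1/1/2.
- Stillbirth plus neonatal: 1.1/2.2/4.4. Three times this is 3.3/6.6/13.2, rounded down to 3/6/13.

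The printed figures therefore follow from the pooled count.

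**Trebling on metformin only, 100 women.** Pooled expectation = 50p + 50 × 3p = 200p, against 100p at background: a doubling.
- Stillbirth plus neonatal: 2.2 + 6.6 = 8.8, not 13.2.
- Maternal: 0.317 + 0.951 = 1.27, not 1.90.

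**Metformin multiple m at which expected deaths equal the trigger t.** (N/2)p + (N/2)mp = t, so m = (t − Np/2)/(Np/2).
- 13 of 100: (13 − 2.2)/2.2 = 4.9.
- 2 of 100 maternal: (2 − 0.317)/0.317 = 5.3.
- At 50 women: 4.5 and 5.3. At 25 women: 4.5 and 11.6.
- An exact trebling of the pooled count gives m = 5.0.

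**Chance of meeting each trigger.** Exact sums of two binomials, one per arm. At 25 women the range covers 12 or 13 on metformin.

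| Women | Stillbirth/neonatal trigger | At background | Trebled on metformin only | Maternal trigger | At background | Trebled on metformin only |
|---|---|---|---|---|---|---|
| 25 | 3 | 10% | 37–39% | 1 | 15% | 27–28% |
| 50 | 6 | 2% | 27% | 1 | 27% | 47% |
| 100 | 13 | 0.05% | 10% | 2 | 13% | 36% |
| At least one band | | 10% | 45–46% | | 30% | 54% |

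The last row follows the cumulative count from 25 to 50 to 100 women and keeps only the paths that have not yet tripped. For maternal deaths this can be done by hand, because not tripping means no death in the first 50 women and at most one in the next 50.
- At background: P(0 in 50) = 0.99366^50 = 0.728 and P(1 in 50) = 0.232, so the chance of tripping is 1 − 0.728 × (0.728 + 0.232) = 30%.
- Trebled on metformin: P(0 in 50) = 0.99366^25 × 0.98098^25 = 0.528 and P(1 in 50) = 0.340, so it is 1 − 0.528 × (0.528 + 0.340) = 54%.

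If both arms trebled, the case the table is built on, 13 of 100 would be reached 57% of the time.

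**What the stated criterion implies.**
- Pooled, twice the expected stillbirth/neonatal count is 2.2/4.4/8.8, rounded up to 3/5/9. Under a trebling on metformin these are met with 37–39%, 45% and 52% probability, and about 66% in at least one band. At background the figures are 10%, 7% and 3%, and about 14% in at least one band.
- Within the metformin arm, three times the expected count is 3 × 50 × 0.044 = 6.6, so 7 of 50. This is met with 50% probability under a trebling and 0.6% at background.
- For maternal deaths, twice the pooled count is 0.32/0.63/1.27, which rounds up to the printed 1/1/2. Three times the count within the metformin arm is 0.95 per 50.

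**Lactic acidosis.** 100 × 4/100,000 = 0.004, ten times the printed figure. For the 50 women on metformin it is 0.002.

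**The case against.** The strongest reply is that the table does what its sentence literally says: it trebles the national rate and applies the result to all women recruited. That stands, so this is not a miscalculated table. But section 11.3 opens by tying the rule to deaths related to the drug, and a pooled trebling is not what a drug-related trebling produces.

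A reader might take the 10% in the last row as showing that the rule cannot detect a trebling. The documents do not support that. The bands apply in succession, so the stillbirth/neonatal rule trips in about 45–46% of trials and the maternal rule in about 54%. If both outcomes trebled independently, at least one would trip about 75% of the time (1 − 0.54 × 0.46). Much of the maternal figure is chance, however, since that rule trips in 30% of trials at background rates. Nor does sensitivity fall steadily as data accumulate: it does for stillbirths and neonatal deaths, but for maternal deaths it rises and then falls.

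Other safeguards exist. Section 9.1 promises the committee interim unblinded data, SAEs are reported within 24–48 hours, and the iDSMC charter, which is not at hand, may hold by-arm rules. These soften the consequence but do not align the table with its criterion. In section 11.3, unblinded review follows a trigger, and section 9.1 gives no threshold.

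The restriction to related deaths does not help either. The thresholds come from all-cause rates, and section 12.4 has causality judged as if every woman were on metformin. Requiring relatedness can only make a halt harder to reach.

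On lactic acidosis, a reader might infer that nothing in the protocol could yield 0.0004. That goes too far: 3.3 per 100,000 patient-years (section 8.8) × 50 women × 12/52 years (entry at 28 weeks, delivery assumed at 40) is about 0.0004. Section 11.3 does not state that reading, and its own inputs give 0.004.

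**Conclusion.** The concern holds as a mismatch between the stated level of concern and pooled triggers. At the final triggers, expected deaths match only at 4.9 times (stillbirth plus neonatal) and 5.3 times (maternal) background on metformin. These are the points where expectation meets the trigger, not strict minima, since chance can trip a trigger at a lower multiple. The effect on performance is moderate: the stillbirth/neonatal rule would respond to a trebling on metformin in somewhat under half of trials, where a table built on the same criterion would respond in about two thirds.

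All of this rests on placebo running at the national rate, complete follow-up, and every death counting towards the trigger. The lactic acidosis figure is a tenfold slip on its own inputs but drives no decision, because any case already prompts review.

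**What to change.** Reconcile the trebling criterion in section 11.3 with the table in one of two ways, the choice being for the sponsor and iDMSC:
- keep pooled counts, but base the triggers on twice the expected number, which is what a trebling on metformin produces; or
- have the iDMSC apply three times the expected number within the metformin arm in its unblinded reports.

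The stillbirth/neonatal figures of 3/5/9 pooled, or 7 of 50 on metformin, illustrate what the protocol's own criterion implies; they are not recommended thresholds. The maternal triggers have the same pooled basis and need the same check. Under the pooled option with rounding up they would stay at 1/1/2; under the by-arm option they would need restating.

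The cost is a change to one table and to the charter. With pooled 3/5/9, the chance of an unnecessary rapid review for stillbirths and neonatal deaths rises from about 10% to 14% over the trial. The by-arm option requires the committee to receive counts by arm, which section 9.1 already foresees.

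Separately, correct 0.0004 to 0.004 per 100 exposed, or 0.002 for the 50 women on metformin.
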